7.4.6 Selection and timing of doses for each patient

Upon completion of the screening assessments and confirmation of patient eligibility, including confirmation of sulfamidase enzymatic activity, patients are assigned a subject number and allocated to a dose cohort in strict consecutive order.

At the time of the first SOBI003 infusion, the patient should not have clinically significant evidence of ongoing infection, as judged by the investigator, or ongoing treatment with antibiotics. In such cases, the first infusion should be postponed until the infection has resolved.

SOBI003 is administered as 4-hour i.v. infusions given once weekly for a duration of 24 weeks. The infusions are administered by qualified health care professionals. Every effort should be made to have the infusions administered every 7th day. A +/- 1-day window is applied after the 4th infusion. Therefore, if the first infusion was administered for instance on a Wednesday, then the 5th to the 24th infusions can be administered on Tuesdays, Wednesdays or Thursdays.

In case of signs and/or symptoms of ongoing infection at subsequent infusion occasions, infusion may be postponed, as judged by the investigator. If the infusion needs to be postponed more than 3 days, then the investigator should discuss with the Sponsor's MD to determine the timing of the next infusion (i.e., whether to await the next scheduled infusion).

Within 30 to 60 minutes prior to each infusion, a single dose of a non-sedative antihistamine should be administered. The antihistamine can either be e.g., cetirizine, levo-cetirizine, loratadine, des-loratadine or fexofenadine, and the administered doses will be in compliance with locally approved labeling. The antihistamine agent is selected at the discretion of the investigator. Antipyretic medication may also be administered, at the discretion of the investigator.

The actual doses of SOBI003 to be administered should be based on the patient's bodyweight at 4-week intervals (i.e., the actual dose administered at Weeks 1 to 4 is based on the bodyweight obtained pre-infusion at Week 1, the actual dose administered at Weeks 5 to 8 is based on the bodyweight obtained pre-infusion at Week 5, etc.). The body weight is obtained either on the day prior to the infusion or the day of infusion.

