In addition, at each time point a sample is collected for immunogenicity, a blood sample is obtained for determination of SOBI003 in serum. In case of a time deviation for the immunogenicity sample, the time for the PK sample should be adjusted accordingly, or an additional PK sample may have to be collected.

Should any patient permanently discontinue SOBI003 treatment prior to Week 24, then a PK and an immunogenicity sample should be obtained as soon as possible after the decision of early treatment withdrawal, as well as 30 to 40 days after the last SOBI003 administration. For

patients with confirmed ADA levels, blood samples for PK and immunogenicity analysis should continue in accordance with Section 7.5.5.3.

The exact time of the SOBI003 infusion start and completion as well as of each PK sampling are recorded in the CRF for each patient.

Sampling, storage and shipment details are provided separately in the study-specific Laboratory Manual.

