15.5 Presentation of concentration data in serum and CSF

15.5.1 Handling of missing data

Missing concentration data for all patients who are administered scheduled study treatment will be considered as non-informative missing and will not be imputed. No concentration estimates will be provided for missing sample values.

For the derivation of the area under the curve (AUC) and for the individual serum concentration versus time curves, the following rules will apply:

- Concentration values below the assay's lower limit of quantification (LLOQ) in pre-dose samples and in samples taken before the time of the 1st quantifiable concentration will be treated as zero; except for the log-transformed concentrations for graphs, where concentration values below the assay's LLOQ in pre-dose samples will be set to LLOQ/2;
- The sampling time of pre-dose samples relative to dosing will also be treated as zero;
- In case a concentration value pre-dose is not available, the concentration value collected at screening may be used for derivation of AUC;
- Post-dose below LLOQ values after the 1st quantifiable time point will be set to missing;
- Samples taken outside the sampling windows may be excluded from by-time point summary statistics; this will be determined prior to database lock.

For serum concentration summary, the following rules will apply:

- Serum concentrations below LLOQ in pre-dose samples and in samples taken before the time of the 1st quantifiable value will be set to zero;
- The serum concentrations below LLOQ after quantifiable concentration will set to missing.

For CSF concentration summary, the following rules will apply:

- CSF concentrations below LLOQ in the pre-dose samples taken before the time of the 1st quantifiable value will be set to zero;
- The CSF concentrations below LLOQ after quantifiable concentration will be summarized.

No further imputation will be applied to any missing values.

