15.6 Attainment of steady state for SOBI003

Aggregate assessment of trough concentrations by repeated measures analysis of variance (ANOVA) may be used to evaluate attainment of steady state and determine the dose number to achieve steady state for SOBI003 (11). The approach is based on the comparison of log-transformed trough concentration values for each dose to the mean of the results for all the following doses.

If data are sufficient to support the analysis, repeated measures analysis will be carried out on log-transformed C_{trough} (pre-infusion concentrations) for Week 2 through Week 24 for each infusion where data available. The following SAS code will be used to conduct the repeated measurement analysis:

```

PROC MIXED
  CLASS dose patient;
  MODEL logCmin = dose;
  REPEATED / TYPE=UN SUBJECT=patient;
  RUN;

```

The trough concentrations observed after Week 2 through Week 24 for SOBI003 for each infusion will be compared with the average trough levels for the rest of the period to determine the time at which steady state was achieved. Contrasts will be tested between a time point and the pooled mean over all remaining time points, such as:

Week 2 pre-infusion value vs. the average of Weeks 2 through 24

Week 3 pre-infusion value vs. the average of Weeks 4 through 24

...

Week 8 pre-infusion value vs. the average of Weeks 12 and 24

Week 12 pre-infusion value vs. the Week 24

The first non-significant comparison will be concluded to be the dosing interval at which steady state concentrations are attained. The p-value for difference of least square means (LSM), LSM ratio, and the 90% confidence interval (CI) for the contrasts will be provided.

Additionally, steady state will be assessed using a mixed model (12) with repeated measures performed on C_{min} ss including dosing interval (Week 2 through Week 24 for SOBI003) as a covariate and subject as a random effect. A random slope effect for dosing interval will also be included. The linear effect of dosing interval on the C_{min} ss over time will be used to assess the assumption of steady state.

```
PROC MIXED data=cminDATASET;
  CLASS subject ;
  MODEL log_Cmin_ss = doseno / ddfm=kr;
  RANDOM intercept doseno /subject= subject;
  RUN;
```

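### SAP 15.6 compares pre-infusion troughs by dose number only, although on-protocol troughs from Week 8 onward can fall 120 to 216 h after the previous infusion

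*SAP*

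**What the plan says.** Protocol 7.4.6 sets the aim: "Every effort should be made to have the infusions administered every 7th day". It then relaxes it: "A +/- 1-day window is applied after the 4th infusion". The window is anchored to the weekday of the first infusion. In the protocol's own example of a Wednesday start, "then the 5th to the 24th infusions can be administered on Tuesdays, Wednesdays or Thursdays". The same section lets infusions be postponed for infection, and calls for discussion with the sponsor only "If the infusion needs to be postponed more than 3 days".

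SAP 15.6 analyses log-transformed troughs ("pre-infusion concentrations) for Week 2 through Week 24 for each infusion where data available") in two ways. A repeated-measures ANOVA contrasts each week with the mean of later weeks ("The trough concentrations observed after Week 2 through Week 24 for SOBI003 for each infusion will be compared with the average trough levels" of the weeks that follow) and takes the first non-significant contrast as attainment of steady state. A random-slope model fits a linear trend. Dose number is the only fixed effect in either.

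Actual times are available. Protocol 7.5.6.1 says: "The exact time of the SOBI003 infusion start and completion as well as of each PK sampling are recorded in the CRF". That section also gives samples labelled 168 h a tolerance of minus 1 h. SAP 15.5.1 adds: "Samples taken outside the sampling windows may be excluded from by-time point summary statistics".

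**The concern.** A trough is a point on a falling curve, so its value depends on how long after the dose it was drawn. If the interval varies between visits and the model knows only the dose number, part of what it sees is visit scheduling.

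The stakes are the steady-state conclusion and the chance of noticing falling exposure. The effect of antibodies on PK is a stated question (Protocol 7.5.5.3, SAP 14.5). The analysis rests on six patients, three per cohort (SAP 4.1), so there is little averaging to absorb timing noise. The steady-state rule also rewards imprecision, because wider contrasts reach non-significance sooner.

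**Working it through.** **1. Allowed intervals.** Interval = 168 h + 24 h × (shift of current infusion − shift of previous infusion). The shift is 0 for infusions 1 to 4 and −1, 0 or +1 day for infusions 5 to 24. This reproduces the protocol's Tuesday/Wednesday/Thursday example.

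- Weeks 2, 3, 4: 168 h.
- Week 5: 168 ± 24 = 144 to 192 h.
- Weeks 8, 12, 16, 20, 24: 168 ± 48 = 120 h (Thursday to Tuesday) to 216 h (Tuesday to Thursday).

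These figures leave out infection postponements. Counting up to 3 days of postponement would give 168 − 24 − 72 = 72 h to 168 + 24 + 72 = 264 h.

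**2. Effect on one trough.** The documents state no half-life, so 24 to 96 h is an assumed range. The factor for a 48 h displacement from 168 h is 2^(48/t½). The true trough accumulation that the analysis is looking for is 1/(1 − 2^(−168/t½)).

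| Assumed t½ | 120 h vs 168 h | 216 h vs 168 h | True accumulation |
|---|---|---|---|
| 24 h | 4.00 | 0.25 | 1.01 |
| 48 h | 2.00 | 0.50 | 1.10 |
| 72 h | 1.59 | 0.63 | 1.25 |
| 96 h | 1.41 | 0.71 | 1.42 |
| 168 h | 1.22 | 0.82 | 2.00 |

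The timing factor exceeds true accumulation up to 72 h, is level with it at 96 h, and is smaller beyond that. These factors are slightly high at long half-lives, because carry-over from earlier on-schedule doses moves by one day only. At 96 h the last dose supplies 1/1.42 = 0.70 of the trough, so the early factor is nearer 0.70 × 1.41 + 0.30 × 1.19 = 1.34.

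**3. How often the extremes occur.** The documents do not say. If the three shifts were equally likely and independent, the interval would be 168 h in 3/9 of visits, one day off in 4/9 and two days off in 2/9. A one-day displacement gives 2^(24/t½) = 2.0, 1.4 and 1.2 at 24, 48 and 96 h.

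**4. Effect on the analysis.** Simulation with six patients, residual SD 20% on the log scale, equally likely shifts, and t-tests on within-patient contrasts and slopes in place of the PROC MIXED contrasts. Each cell shows troughs fixed at 168 h, then troughs with the window.

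| Assumed t½ | SD of log(Week 24/Week 2) | Slope test detects a 2.5%-per-week fall | Week 2 contrast non-significant despite that fall |
|---|---|---|---|
| 24 h | 0.27, 0.82 | 100%, 39% | 43%, 64% |
| 48 h | 0.27, 0.45 | 100%, 81% | 71%, 75% |
| 96 h | 0.27, 0.31 | 97%, 87% | 85%, 86% |

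The simulated fall totals exp(−0.025 × 22) = 0.58 by Week 24, that is, 42%.

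With no real change and a 24 h half-life, the slope test is significant in about 5% of runs with or without the window, so random shifts do not create false trends. They do scatter the estimate. The Week 24/Week 2 ratio lies outside 0.80 to 1.25 in 54% of runs with the window against 5% without (24 h), and 29% against 15% (48 h). If 70% of infusions fall on the nominal day, the figures with the window are 34% and 23%.

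**5. Whether anything else corrects for this.** Protocol 7.5.6.3 uses exact sampling times in the non-compartmental calculations, but they do not enter the SAP 15.6 models. SAP 15.5.2 lists actual times and deviations only. The optional exclusion in SAP 15.5.1 covers summary statistics and out-of-window samples, and a 216 h trough before an on-schedule infusion is not clearly out of window.

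**The case against.** The case for leaving the plan alone has substance. Every effort is to be made to keep the 7-day interval, and no document says how often visits shift. The ANOVA is conditional on sufficient data. AUC over 168 h and clearance at Weeks 1, 4, 12 and 24 show exposure without relying on a single trough, and population PK is planned. All of this stands and limits the importance of the point. It does not put elapsed time into the models, and the random-slope model is planned without that condition.

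Several stronger readings are tempting, but the documents do not support them:

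- *Visit timing will produce a false trend.* Random shifts add noise. A spurious rise or fall needs shifts that line up across patients, which is possible with three per cohort but is not the expected result.
- *Timing error sits only on the later side of each contrast.* Weeks 8, 12 and 24 are all exposed, so this fails for Week 8 against Weeks 12 and 24, and for Week 12 against Week 24.
- *The trough accumulation ratio is distorted.* SAP 15.5.4 compares last with first dose. The first-dose trough precedes infusion 2, before the window opens. The last-dose trough is the Week 24 Day 8 sample, with its minus 1 h tolerance.
- *The optional exclusion would remove most later troughs.* It does not govern the SAP 15.6 models.
- *The predicted Cmax and AUC make the problem far larger.* They imply an effective half-life of about 7.4 to 7.9 h and a factor of about 84. But 168 h would then be about 21 half-lives, and troughs would probably be unquantifiable.
- *The minus 1 h tolerance conflicts with the infusion window throughout.* It applies only to samples labelled 168 h. The conflict arises where such a sample doubles as the next pre-infusion sample with the window open: Weeks 5, 13, 17 and 21 (Protocol Table 6, SAP Table 3).

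**Conclusion.** The point holds as a gap in SAP 15.6 that is cheap to close. The 120 to 216 h range follows directly from Protocol 7.4.6, and neither steady-state model accounts for it. The main consequence is lost precision: real change is harder to see, and the decision rule leans towards declaring steady state. The loss is large at an assumed half-life of 24 h, moderate at 48 h and small at 96 h. The pull on the first contrast is marked only at 24 h. These sizes rest on an assumed half-life range, an assumed 20% residual SD and an assumed shift pattern, none of which the documents supply. The primary safety endpoint and the trough accumulation ratio are not materially affected.

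**What to change.** 1. In SAP 15.6, add actual hours since the start of the previous infusion, centred at 168 h, as a continuous covariate in the random-slope model. Add it to the repeated-measures ANOVA where that model can be fitted. An unstructured covariance over seven visits has 7 × 8/2 = 28 parameters, and six patients may not support it with or without the covariate.
2. Show elapsed hours beside each trough in the by-visit summaries and in the trough figures.
3. Repeat the analysis on troughs within a band around 168 h fixed before data review, as a sensitivity analysis. A mandatory exclusion would be costly: with equally likely shifts, a band of a few hours would remove 6/9 of later troughs. Under SAP 15.5.3, one missing value among three patients in the terminal phase can suppress a mean.
4. Reconcile the minus 1 h tolerance for 168 h samples with the infusion-day window where the sample doubles as pre-infusion (Weeks 5, 13, 17 and 21).

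The cost is SAP wording and one model term, using times already recorded in the CRF. The covariate assumes a common per-hour decline across patients, which may not hold if antibodies change clearance in some of them. Items 1 to 3 need no change to the dosing window.

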- p Blood sampling for only hsCRP, IL-1ra, TNF α , IgE, and tryptase. Baseline sample analyzed only in case acute infusion/anaphylactic reaction occur during SOBI003 treatment to facilitate the determination of reaction etiology.
- q Frequent PK blood sampling is conducted at Weeks 1, 2, 3, 4, 5, 8, 12, 13, 16, 20, and 24. Samples are also collected before start of infusion and at completion of the infusion at Weeks 2, 3 and 8 and before start of infusion, completion of infusion and at 168 hours (Day 8) at Week 16 and 20. PK blood sampling will be

adjusted based on the patient's bodyweight in order not to exceed blood draw volume limits. At Baseline, the PK and immunogenicity samples should be taken on the day of CSF sampling for HS analysis. Details on PK blood sampling are given in CSP Table 6.

- r Sleep pattern is assessed by actigraph recordings for 7 consecutive days at Baseline and within 2 weeks prior to Week 12 and 24, i.e., Baseline assessment should preferably be completed prior to any anesthetic/sedation is applied and prior to PK and HS blood samplings. The aim should be to have the recordings completed during normal patient sleeping conditions and prior to the SOBI003 infusions on Day 1 at Weeks 12 and 24. A sleep diary is completed during the days of actigraphy. Parents should complete the CSHQ upon completion of each actigraph assessment
- s In case both BSID-III and KABC-II are to be administered, there should be at least 2 days between the assessments. Attempts should be made to have the assessment(s) performed at least 5 days after any anesthesia/sedation. The Baseline assessment should be completed within 2 weeks prior to the first SOBI003 infusion.
- t The Baseline assessment should be completed within 2 weeks prior to the first SOBI003 infusion.
- u Blood samples for immunogenicity and HS and urine sample for HS should be collected pre-infusion.

Table 2 Detailed schedule of events – Weeks 1 to 4

Day	Weeks 1, 2, 3 and 4												
	1	1	1	1	1	1	1	1	1	1	2	3	5
Time	Pre-inf	0	1:00	2:00	3:00	4:00	4:01 - 5:00	6:00 – 7:00	8:00 - 12:00				
Medical history	X ^a												
Eligibility criteria	X ^a												
Prior & concomitant medication	X	X	X	X	X	X	X	X	X	X	X	X	X
Physical examination ^b	X		X	X	X		X	X	X	X	X	X	X ^d
Weight	X ^c												
Vital signs ^l	X		X	X	X		X	X	X	X	X	X	X ^d
Continuous pulse-oximetry ^e	→	→	→	→	→	→	←						
12-lead ECG	X						X						
Antihistamine ^f	X												
SOBI003 administration:													

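### The steady-state contrasts listed in SAP 15.6 do not follow the SAP's own rule: Week 2 sits in its own comparator, and the late contrasts omit scheduled troughs

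*SAP*

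**What the plan says.** SAP 15.6 describes a repeated-measures ANOVA on log trough concentrations. The principle is a "comparison of log-transformed trough concentration values for each dose to the mean of the results for all the following doses". The data scope is pre-infusion concentrations "for Week 2 through Week 24 for each infusion where data available". The contrasts are introduced by "Contrasts will be tested between a time point and the pooled mean over all remaining time points, such as", and four are then written out, with an ellipsis between the second and third:

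- The opening line reads "Week 2 pre-infusion value vs. the average of Weeks 2 through 24", so its comparator begins with the very week under test.
- The line below it reads "Week 3 pre-infusion value vs. the average of Weeks 4 through 24", so here the comparator begins one week after the week under test.
- After the ellipsis comes "Week 8 pre-infusion value vs. the average of Weeks 12 and 24", which is a comparator of two weeks.
- The closing line is "Week 12 pre-infusion value vs. the Week 24", which leaves a comparator of one week.

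The first non-significant contrast marks the dosing interval at which steady state is declared. For each contrast the SAP promises a p-value, the ratio of least-squares means (LSM) and a 90% CI. The model code uses an unstructured within-patient covariance (TYPE=UN).

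The sampling schedule is richer than the late contrasts suggest. Footnote q to SAP Table 1 has PK samples "before start of infusion, completion of infusion and at 168 hours (Day 8) at Week 16 and 20", and SAP Table 7 schedules these in all three weight bands. Footnote h to SAP Table 3 states that the 168-hour samples after the Week 12, 16 and 20 infusions are the pre-infusion samples of Weeks 13, 17 and 21.

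**The concern.** There are two departures from the stated rule.

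First, the Week 2 comparator includes Week 2. The Week 3 line directly below starts its comparator one week later, as the rule requires, so the Week 2 line disagrees with both the rule and its neighbour. Part of the Week 2 value is subtracted from itself, and the reported ratio and interval are pulled towards 1. Week 2 therefore looks closer to the later level than it is.

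Second, the Week 8 and Week 12 comparators are written out in full and contain none of the troughs scheduled at Weeks 13, 16, 17, 20 and 21. Because failure to reach significance is read as steady state, a comparator built on fewer weeks than are available makes that declaration easier. Nor does any listed contrast start at Weeks 13 to 21. If Week 12 still differed from Week 24, the list would offer no later point at which to place steady state, although the samples exist.

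**Working it through.** **Inputs.** SAP Table 7, read with footnote h to SAP Table 3, gives these pre-infusion trough weeks from Week 2 to Week 24: 2, 3, 4, 5, 8, 12, 13, 16, 17, 20, 21, 24, so k = 12. The weeks named or implied in the contrast list are 2, 3, 4, 8, 12, 24, so k = 6. SAP 4.1 gives 6 patients (3 in each of two cohorts). The SAP states no variance or correlation for troughs, so the precision figures in step 3 rest on an assumption.

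**Step 1: algebra of the Week 2 line.** Let W2 be the Week 2 LSM on the log scale and M the equally weighted mean of the k − 1 later LSMs. Then

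W2 − [W2 + (k − 1)M]/k = ((k − 1)/k) × (W2 − M).

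The listed contrast is a constant multiple of the intended one. Estimate, standard error and CI limits on the log scale are all multiplied by (k − 1)/k, so the t-statistic and p-value do not change. A simulated check with 6 patients gave identical t and p for the two versions.

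**Step 2: size of the shrinkage.**

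- k = 12: factor 11/12 = 0.917, a shrinkage of 8.3%. A true ratio of 0.67 is shown as 0.67^(11/12) = 0.69.
- k = 6: factor 5/6 = 0.833, a shrinkage of 16.7%. A true ratio of 0.67 is shown as 0.67^(5/6) = 0.72.
- For other values, a true 0.50 is shown as 0.53 (k = 12) or 0.56 (k = 6), and a true 0.80 as 0.815 or 0.83.

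**Step 3: precision of the late contrasts.** Assume equal, independent within-patient errors. The standard error of one week against the mean of m later weeks is then proportional to √(1 + 1/m).

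- Week 8 as listed, against Weeks 12 and 24 (m = 2): √1.5 = 1.225. Against Weeks 12, 13, 16, 17, 20, 21 and 24 (m = 7): √(8/7) = 1.069. Ratio 1.225/1.069 = 1.15.
- Week 12 as listed, against Week 24 (m = 1): √2 = 1.414. Against Weeks 13, 16, 17, 20, 21 and 24 (m = 6): √(7/6) = 1.080. Ratio 1.414/1.080 = 1.31.

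**Step 4: can the coded model carry all the weeks?** An unstructured covariance over 12 weeks has 12 × 13/2 = 78 parameters. Six patients with complete data give 6 × 12 = 72 observations. The count falls further for any patient in the lowest weight band, where Table 7 has no Week 3 pre-infusion sample.

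**The case against.** The strongest reply is that the governing text already settles both points. The rule refers to following doses, the scope takes in every infusion with data, and the four lines are offered as examples with an ellipsis. A programmer working from the rule would start the Week 2 comparator at Week 3 and bring in the later troughs. Much of this stands. A reader might infer that the SAP will discard the Week 13 to 21 troughs; the documents do not support that, because the scope statement covers them. What remains is that the Week 8 and Week 12 comparators are spelled out and conflict with the rule, so two programmers could produce different tables from the same paragraph.

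A reader might also infer that the Week 2 slip changes the steady-state decision. It does not, by step 1: the decision uses significance, and the p-value is unchanged.

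A third tempting inference is that the list was simply carried over from the protocol's older sampling schedule. Protocol Table 6 already collected a Week 13 pre-infusion sample, so that schedule cannot explain its absence. The named weeks do match the protocol's list for pre-dose concentration in section 7.5.6.3, but a link is conjecture.

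It is also fair to say that the ANOVA is conditional on sufficient data, that a separate random-slope model in the same section uses none of these contrasts, and that steady state is not a listed endpoint. These limit the importance of the point. Finally, adding all the troughs while keeping the unstructured covariance would not work. That objection stands, and the correction has to deal with it.

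**Conclusion.** The point holds as a minor correction to a supporting PK analysis. The Week 2 line is wrong by the SAP's own rule and would misstate a reported estimate and interval, shrinking the log ratio by about 8% to 17% depending on which troughs enter; this assumes equal weights across weeks. The Week 8 and Week 12 lines are inconsistent with the rule and the schedule. If they are followed, their standard errors are about 15% and 31% larger than with all later troughs. Those two figures depend on equal, independent within-patient errors and are not established for the covariance model actually coded. The direction matters more than the exact size: lower precision favours declaring steady state under a rule that rests on non-significance.

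**What to change.** In SAP 15.6:

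1. Change the Week 2 comparator to the average of Weeks 3 through 24.
2. Define every contrast against all later scheduled pre-infusion troughs, drawn from Weeks 3, 4, 5, 8, 12, 13, 16, 17, 20, 21 and 24. This adds contrasts starting at Weeks 13, 16, 17, 20 and 21, the last being Week 21 against Week 24. Note that the lowest weight band has no Week 3 pre-infusion sample.
3. Replace TYPE=UN with a simpler named structure, for example compound symmetry or a spatial-power structure suited to the unequal spacing of weeks, with Kenward-Roger degrees of freedom (which the SAP already uses in its second steady-state model).

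The cost is SAP wording and a small change to the model code; no new data are needed. The downside is that a covariance structure must be assumed.
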